**Exercise**. Mounting evidence suggests that moderate physical activity can be used as a treatment to improve and/or prevent cognitive decline. The majority of this evidence comes from animal models and older adults.  In non-HIV infected older adults, observational and epidemiological reports have shown a significant relationship between level of physical activity and cognitive function implying that exercise may have a neuroprotective effect on later life cognition. For example, Yafee found cognitive performance improved with increasing physical activity levels. Fitness training in meta-analytic studies show robust, selective gains for cognition, with executive-control processes showing greatest benefit (moderate effect size of 0.48). Cognitive and physical function as well as positive behavior among older adults with dementia or other forms of CI also show significant improvements (e.g., effect size of 0.62 across all outcomes in meta-analysis) with physical exercise.  Collectively, intervention studies conducted in older adults favor a causal relationship between aerobic exercise and improved cognition, more efficient brain functioning and less brain volume loss. Evidence from other populations, including those with disabilities and chronic illness, (e.g. renal failure, Parkinson's Disease, multiple sclerosis, stroke, Alzheimer's Disease) suggests that exercise improves cognition via several biological processes: its impact on increased cerebral blood flow and oxygen delivery; its influence on BDNF (thought to enhance neurogenesis); and its effect on certain neurotransmitters. Our preliminary work indicated that participants with better physical function had less difficulty with memory and concentration than those with poorer physical function. Exercise is reported to improve cerebral oxygenation following moderate intensity aerobic exercise, but few studies have examined this directly in clinical populations or the impact on cognitive functioning in well-designed studies. As stated above, the effect of exercise is much greater on selected cognitive processes, especially executive function suggesting it may be amenable to intervention. This finding has important implications for OPLWH whose executive functioning is particularly affected by the underlying pathological changes associated with HIV. Only one study has examined the effect of exercise on cognitive functioning in HIV infected individuals. Filipas et al., reported a significant 14 point improvement in self-reported cognitive function using the Medical Outcomes Study HIV Survey in HIV infected men a following a 6 month exercise training program. However, self-report cognitive functioning measures are highly influenced by fluctuations in mood and are often invalid when objective neuropsychological testing is conducted. The effects of aerobic exercise on neurocognitive function in OPLWH using standard, objective neuropsychological testing has not been reported to our knowledge. Mechanisms by which exercise may improve cognitive functioning among OPLWH include improved physical function, anti-inflammatory responses, and blood flow and oxygenation as well as reduced CVD symptoms.  Increasing age and BMI are associated with poorer cardiorespiratory fitness in HIV-infected populations, which in turn increases risk for CVD and adverse cardiac events. Reductions in CRF have primarily been attributed to sedentary behavior and lifestyle habits. For example, PLWH often exhibit maximal oxygen consumption (VO2) that is 24% - 44% below their age-predicted normal values for cardiorespiratory fitness and up to 50% fail to meet daily recommended physical activity guidelines. Short duration studies have shown significant increases in cardiorespiratory fitness with moderate or high intensity exercise training in as little as 6 weeks, in addition to a dose response to aerobic exercise when performed at least 2-3 times per week. Other beneficial physiological and anthropometric adaptations include increased serum HDL-C, decreased triglycerides, reduced abdominal circumference and total cholesterol, but the metabolic outcomes have been inconsistent and long-term evaluation of exercise has not been reported. Exercise has also been associated with improved inflammatory, vascular and endothelial outcomes in non HIV infected persons, but has not been well studied in PLWH, and no studies have specifically evaluated these variables in OPLWH. In one study, endurance and strength training decreased plasma IL-18, whereas aerobic exercise alone also decreased other inflammatory markers (TNF-alpha, IL-6, and hs-CRP) in 39 HIV infected men whose mean age was  $53\pm 8$  years. Psychological well-being and quality of life (QoL) in PLWH have also reportedly improved following exercise interventions, similar to that reported in non HIV infected individuals. Evidence shows that exercise can reduce depression and fatigue which are common symptoms that considerably lowers OoL in PLWH. For instance, up to 50% of PLWH experience depressive symptoms. Whether these symptoms persist, worsen or may be improved in OPLWH is less clear.

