# 4. Objectives

Our home-based aerobic exercise intervention, the '*Let's Move Program*' has been tested and is effective for lowering CVD risk in previous trials of older caregivers and adults with advanced CVD. The proposed efficacy trial, Fit BRAiN will recruit 200 PLWH and randomize them (2:1) to either the *Let's Move intervention* (n=132) or an attention control condition, *Let's Flex* (n=68), and follow them for an additional 3 assessments/time points (at 13-15 weeks post baseline, 28-30 weeks post baseline and again at 56-58 weeks post baseline). Participants will be  $\geq$  50 years of age, sedentary, demonstrate objectively measured CI, and stable on antiretroviral medications for at least 6 months. Motivational Interviewing (MI) will be used to promote exercise self-efficacy and optimize adherence to the intervention and flexibility and stretching to the attention control arm. The following are our aims:

AIM 1: To test, in a RCT, the efficacy of the *Let's Move Program* to improve cognitive functioning in this sample.

H0 1: Participants in the *Let's Move* intervention will have significantly higher scores than participants in the Let's Flex attention control group on measures of executive skill, episodic memory, and information processing speed at 3 assessments/time points (averaging a total of 56-58 weeks) post-baseline.

**AIM 2:** To test, in a RCT, the impact of the *Let's Move Program* on inflammatory markers, endothelial vascular function, and neuronal growth factor (BDNF) in this sample.

H0 2: Participants in the *Let's Move* intervention will demonstrate improved *inflammatory markers, neuronal growth factor, oxidative stress, thrombotic tendency, and endothelial vascular function* compared to the Let's Flex attention control group at 3 assessments/time points (averaging a total of 56-58 weeks) post-baseline.

**Secondary Aim:** To explore the potential mediation effects of inflammatory biomarkers, endothelial vascular function, and neuronal growth factor on the relationship between the *Let's Move Program* and the cognitive skills measured in Aim 1.

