### Study Assessments.

Cognitive Outcome Measures will be used to measure the primary outcome variables at BL, T1, T2 and T3 assessments. Cognitive outcome measures will be measured at the second visit for baseline after the study cardiologist has cleared a participant to continue with the exercise study after reviewing their EKG from a treadmill stress test. These outcome measures have been effectively used to examine neurocognitive functioning and treatment effectiveness in numerous clinical trials and in persons with wide-ranging medical conditions, including those who have HIV/AIDS. Table 4 lists the selected measures for the proposed study, domains assessed, a brief description of each, primary variable(s), and administration time. The outcome measures reflect the areas of executive functioning, episodic memory, and processing speed hypothesized to be affected by the exercise intervention based on findings in the research literature. Four parallel forms are available for the memory measures to reduce potential practice effects associated with repeated presentation of the same to-be-learned stimuli. [name], the project neuropsychologist, will provide outcome assessment training and continuous monitoring of data collection and quality. The examiner will code the reliability of each test score, any alteration of standard procedure, and the reason.

Table 4. Cognitive Outcome Measures			
Measures	Description	Time (min.)	
Stroop Color and Word Test	The Stroop Color and Word Test consists of a Word Page with color words printed in black ink, a Color Page with 'Xs' printed in color, and a color-Word Page with words from the first page printed in colors from the second page (the color and the word do not match). The respondent goes down each sheet reading words or naming the ink colors as quickly as possible within a time limit. The test yields three scores based on the number of items completed on each of the three stimulus sheets		
Trail Making Test A & B	The Trail Making Test is a neuropsychological test of visual attention and task switching. It consists of two parts in which the subject is instructed to connect a set of 25 dots as quickly as possible while still maintaining accuracy. The test can provide information about visual search speed, scanning, speed of processing, mental flexibility, as well as executive functioning. It is sensitive to detecting several cognitive impairments such as Alzheimer's disease and dementia		

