Letter Fluency	(FAS) The FAS test requires stating out loud as many words that begin with the assigned letter as possible within 60-seconds.		
Category Fluency	(Animals) The Category fluency test requires stating out load the names of as many animals as possible within 60-seconds.		
Hopkins Verbal Learning Test - Revised	This is a list learning task requiring the respondent to recall as many words as possible from a list of 12 words provided orally by the examiner. There is a learning trial, a delayed recall trial, and a recognition trial.		

Brief Visual Memory Test - Revised	This test is a non-verbal equivalent to the HVLT-R and requires that respondents reproduce simple visual images from memory (the images are displayed for 10 seconds then removed). The BVMT-R contains a learning trial, a recall trial, and recognition trial, and a copy trial.	
Grooved Pegboard	This test requires the placing of grooved pegs into a same-shaped hole as quickly as possible, once with the dominant hand and once with the non-dominant hand.	
Finger Tapping Test	This test a fine motor speed requires tapping a lever with the index finger as quickly as possible. Trials with the dominant and non-dominant hand are completed.	
Coding	This test requires writing the corresponding symbol associated with a letter from a key provided. As many responses as possible are completed in the 120 second time limit.	
Digit Span	The digit span test requires repeating an increasing span of digits that are provided verbally by the examiner. The test includes trials of repeating digits in the same order presented by the examiner and in the reverse order of that presented by the examiner.	
Spatial Span	Spatial span requires repeating in both forward and reverse order, the sequential order of blocks presented by the examiner.	
Symbol Span	Working memory, Letter-number sequencing. The subtest assesses visual working memory using novel visual stimuli. A series of abstract symbols on a page are shown briefly. Then the symbols are to be selected from an array of symbols in the same order they were presented on the previous page.	
Instrumental Activities of Daily Living (IADL)	This is a self-report measure assessing the amount of assistance, if any, required to do day-to-day tasks necessary to live independently.	

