NIH Toolbox	Computerized cognitive tests developed and distributed by the NIH. Tests include Pattern Comparison Processing Speed Test, Picture Vocabulary Test, Reading Recognition Test, Dimensional Change Card Sort Test, Flanker Inhibitory Control and Attention Test, Picture Sequence Memory Test, List Sorting Working Memory Test, and Oral Symbol Digit Test	

Blood collection procedures: After overnight fasting, all blood samples will be collected with an intravenous (IV) catheter will be placed into a forearm vein or hand. Blood samples will be collected by a research staff or laboratory assistant trained in blood drawing techniques after 30 minutes of rest between 8-11:30 am (to control for circadian variation) in EDTA or Heparin tubes and immediately placed on ice. Where indicated, blood will be spun at 3,000 rpm for 15 minutes at 4C. Plasma samples will be coded, labeled and will be aliquoted into pre-cooled siliconized polypropylene tubes and stored at -80C until assayed for relevant biomarkers. Processing and analyses of specimens will be performed according to manufacturer ELISA recommendations. Blood collection for the measures in Table 5 will occur at **Baseline, T1, T2 and T3 assessments.** When the study is completed, the blood sample will be destroyed.

Flow mediated Dilation (FMD): A forearm test will be conducted to measure endothelial function at **Baseline, T1, T2, and T3 assessments** after overnight fasting. Participants will have a blood pressure cuff placed around one of their arms. The blood pressure cuff will be inflated and deflated and a trained clinical staff will use an ultrasound device to take measurements of the blood flow in the participants arm.

Table 5. Biological Measures			
Measures	Description		
Inflammatory Biomarke	rs		
Soluble Cluster of Differentiation 14 (sCD14)	Marker of monocyte activation, is associated with neurocognitive impairment and HANDs and higher mortality in PLWH. 		
Interleukin 6 (IL-6)	IL-6 is a well-established pro-inflammatory cytokine known to contribute to the pathogenesis of insulin resistance that contributes to increased risk of CVD and CI through inflammation and promotion of endothelial vascular dysfunction. IL-6 has also been associated with both depression and fatigue in both medically ill and medically healthy individuals. 		

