#### 7. Statistical Analysis.

**Phase 3 Data Analysis**. The objectives of phase 3 are to: 1) maintain data files; 2) evaluate study outcomes; and 3) disseminate study results and project materials.

**Data management** Procedures for data management and monitoring will be initiated during the start-up phase. The project coordinator will coordinate the organization and processing of forms, and schedule and implement checks of data quality and completeness. Data from the ACASI files will be saved in the database. Data will be backed up on a regular basis to prevent loss of data. Data will be transferred electronically from the sites to a secure password protected network drives where it will be checked and downloaded. A data-checking plan based on each questionnaire will be used to look for suspicious entries. Data monitoring will be merged as necessary to answer the research questions. [name] will oversee the final quality assurance/quality control data reviews. She will design and conduct the statistical analyses; assist as needed with designing research forms and data entry; and collaborate with the investigators on analysis and interpretation. We have successfully used these procedures in our research projects.

**Sample size and Power Calculation.** For longitudinal analyses of cognitive functioning and biological measures (Aims 1 and 2), our sample size provides adequate power (80%) to detect effect sizes of 0.37 or larger at alpha=0.05. Our ongoing study (Caregiver Stress study) showed that between-group effect sizes related to exercise vs. AC groups are on the order of 0.5 to 0.8 for physiological, physical and psychological functions.

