Statistical Analyses. General Considerations in Statistical Analyses: Our initial data exploration will include: 1) determining the distributions of outcome measures and assessing whether data transformations are needed, 2) insuring that the underlying assumptions of statistical analyses are satisfied, 3) identifying potential co-linearity problems, and 4) identifying potential outliers that require further investigation. For categorical variables, we will check for sparse cells and regroup categories if necessary. In building statistical models, we will check linearity assumptions for continuous predictors and consider higher-order terms if needed. *Missing* Data. We will make every effort to minimize missing data by monitoring the degree of missing data regularly and implementing successful methods for obtaining follow-up data. When data cannot be collected, sensitivity analysis will be performed to evaluate the impact of missing data on results. We also plan to use restricted maximum likelihood (REML) method for estimating the longitudinal statistical models to minimize the impact of missing data. This will make it possible to retain cases with partial data while making less restrictive assumptions about missing data patterns. Controlling for Confounding. Our analyses will account for potential confounding factors such as medications, gender, BMI and other specific confounders for each aim. Adjustment for stratification variables. We plan to adjust for the stratification variable, i.e. study site, in the statistical analysis. This will correct for correlation between the treatment groups due to the balanced randomization within each site and consequently provide better statistical power in detecting differences between treatment groups. Adjustment for Multiple Measures and Comparisons. We will apply adjustments such as Bonferroni correction when appropriate to adjust for multiple comparisons. A combination of statistical software will be used for statistical analysis and data visualization, including SPSS (v.20), SAS (v. 9.3), and R (v. 3.0.1). All statistical tests will be two-sided and intent-to-treat procedures will be employed.

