AIM 1. Neurocognitive Improvement: We expect the primary cognitive improvements to be found in executive skill, episodic memory, and processing speed (as measured by CANTAB) since these skills are most susceptible to the effects of exercise. As recommended by Grant and Marcotte, demographically adjusted scores will be used to test for intervention effects between the treatment and attention control conditions over the study time period. To adjust for the effects of practice from repeated testing, we develop z-scores for each of the neuropsychological assessment tests using the regression-based method. Specifically, we first use multiple regression from control participants' test scores to derive the norms for change across visit times. Then we calculate the z-score by adjusting the raw test score with the expected normal follow-up score based on the subject's baseline characteristics using the multiple regression model. This method accounts not only for the effects of practice but also test-retest reliability (e.g., regression to the mean, ceiling and floor effects) and is the method suggested for use with clinical samples. The z-scores will be used as the outcome measures in the following statistical analyses. We will then use the confidence-interval-based method to classify whether a subject has shown improved cognitive functioning when comparing to the norms for change. Specifically, we will define "no change" on each cognitive test using a 90% confidence interval (CI) based on the norms generated from the control subjects' data. Then, participants who score above the upper bound of the 90% CI, i.e. in the top 5% of the normal distribution, will be defined as "improved", while those within the 90% CI defined as "no change" and those below the lower bound of the CI defined as "decliners". Modeling and Hypothesis testing. Repeated measures analysis will be performed to model the z-scores of the NP tests, the classified improvement status and other outcome measures longitudinally to test whether there are differences between the two intervention groups in terms of executive skill, episodic memory and information

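### H0 1 is about three cognitive domains, but the Aim 1 analysis models each test separately and gives no rule for turning several test results into one domain result

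*Combined protocol and SAP*

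**What the plan says.** **Hypothesis.** Section 4 (Objectives) states H0 1 for "executive skill, episodic memory, and information processing speed at 3 assessments/time points": three domains, with no individual test named.

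**Measures.** Section 5 (Study Assessments) makes the Table 4 battery the source of the primary outcomes and says: "The outcome measures reflect the areas of executive functioning, episodic memory, and processing speed hypothesized to be affected". Table 4 has 13 instruments, one of them the IADL scale, plus the NIH Toolbox with eight tests ("Tests include Pattern Comparison Processing Speed Test, Picture Vocabulary Test, Reading Recognition Test" and five others). Grooved Pegboard and Finger Tapping are motor tests, and vocabulary and reading are not among the three domains. The IADL scale also appears in Table 6 as functional status.

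**Analysis.** In Section 7 (Aim 1), "we develop z-scores for each of the neuropsychological assessment tests using the regression-based method". Those z-scores become the outcomes of the mixed models, which are then said to compare the arms on the three domains. Averaging, a lead test for each domain, or any other combining rule does not appear. The same paragraph says the domains are measured by CANTAB, which Table 4 does not list.

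**Error control and power.** Section 7 allows Bonferroni-type adjustment where suitable, without naming a family or a number of tests. It adds: "All statistical tests will be two-sided and intent-to-treat procedures will be employed". The power statement uses unadjusted alpha: "our sample size provides adequate power (80%) to detect effect sizes of 0.37 or larger at alpha=0.05".

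**The concern.** A claim that exercise improved, say, episodic memory would have to be read off several separate test results, and the plan does not say how. One significant test, a majority, or all of them could each be taken as support, and the choice could be made after the results are seen.

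The two obvious ways of proceeding both cost something. Without correction, about 20 tests make a chance positive likely. With correction over all of them, each test loses much of its power, and part of the alpha goes to measures that H0 1 does not mention. In neither case is the domain hypothesis tested directly.

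**Working it through.** **Step 1: count the tests.** Thirteen instruments plus eight Toolbox tests give 21 entries, or 20 without IADL. Splitting Trails A and B adds one to either count. The figures below use m = 21. This family is an assumption, since the plan names none.

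**Step 2: try to reproduce the stated 80% at 0.37.** For a plain two-sided comparison, power = Φ(0.37/√(1/n₁+1/n₂) − 1.960).
- 132/68: Φ(0.37/0.1493 − 1.960) = 69.8%
- 107/53: Φ(0.37/0.1680 − 1.960) = 59.6%
- 85/43 (128 split 2:1): 50.7%

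None gives 80%. A one-sided test with 132/68 gives 79.8%, but the plan is two-sided. Averaging three follow-up visits would also reach 80%, given a visit-to-visit correlation of 0.67, 0.43 or 0.25 for the three sizes respectively. The plan states neither that correlation nor which sample size was used, so the 80% can be neither confirmed nor called wrong. It is taken as given below, which fixes the noncentrality at 1.960 + 0.842 = 2.802 for d = 0.37.

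**Step 3: single test, Bonferroni over 21.** The critical value for 0.05/21 is 3.04. Power = Φ(2.802 − 3.04) = 40.7% (41.2% for m = 20, 40.1% for m = 22).

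**Step 4: three domain means at 0.05/3.** The critical value is 2.394. Averaging k tests with equal effects and common correlation r multiplies the standardised effect by g = √(k/(1+(k−1)r)). Power = Φ(2.802·g − 2.394). Both k and r are assumptions.
- r = 1 (g = 1, alpha split only): 65.8%, or 1.62 times 40.7%
- k = 4, r = 0.5 (g = 1.265): 87.5%, or 2.15 times
- k = 3, r = 0.8: 73.1%; k = 5, r = 0.2: 98.9%

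**Step 5: other effect sizes.** Section 7 cites 0.4 to 0.6 for cognition. The noncentrality becomes 2.802·d/0.37.

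| d | One test, 0.05/21 | Domain mean, k = 4, r = 0.5, 0.05/3 | Ratio |
|---|---|---|---|
| 0.37 | 40.7% | 87.5% | 2.15 |
| 0.4 | 49.6% | 92.5% | 1.86 |
| 0.5 | 77.3% | 99.2% | 1.28 |
| 0.6 | 93.4% | about 100% | 1.07 |

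**Step 6: a fairer comparator.** Suppose a domain counts as positive when any of its tests passes 0.05/21. Simulation at d = 0.37 (assumed 3 to 6 tests per domain, correlation 0.5 within and 0.3 between domains) gives 66–79% per domain, against 85–90% for the domain mean. The ratio is about 1.15 to 1.3.

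**Step 7: dilution.** With k = 4, r = 0.5 and only j tests responding at 0.37, power = Φ(3.544·j/4 − 2.394). This is 60% for j = 3, 27% for j = 2 and 7% for j = 1.

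**Step 8: no correction.** If all 21 tests were null and independent, the chance of at least one positive is 1 − 0.95²¹ = 66%. Positive correlation between tests would lower this.

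**The case against.** The strongest objection is to any claim that domain scores would about double the power. A reader might infer that from Step 4, but the documents do not support it as a general statement. It requires Bonferroni over all 21 tests, which the plan never specifies, one single test as comparator, an effect near 0.37 that is equal on every test, and a correlation the documents do not give. At 0.5 to 0.6, the upper part of the plan's own range, single tests keep 77–93% power, so they are not badly underpowered there. Against an any-test rule the gain is modest. If only one or two tests of a domain respond, averaging loses power. All of this stands.

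A reader might also see a contradiction in the IADL scale, because the Introduction warns that "self-report cognitive functioning measures are highly influenced by fluctuations in mood". That does not follow. The warning concerns self-reported cognition, whereas Table 4 describes IADL thus: "This is a self-report measure assessing the amount of assistance, if any, required to do day-to-day tasks". The scale measures function, and nothing says it would be given a z-score as a neuropsychological test. The valid remark is only that it lies outside the three domains.

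Finally, the text before Table 4 promises domains and primary variables for each measure, and such a column may have been lost when the PDF was converted to text. The absence of a test-to-domain map therefore cannot be asserted firmly. A map would still not say how several results in a domain become one.

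**Conclusion.** The mismatch stands: the hypothesis is at domain level, the outcomes are at test level, and the available text has no rule linking them. This does not depend on any power figure. The unreconciled CANTAB reference leaves the set of Aim 1 tests itself uncertain.

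The size is conditional. At 0.37, with the stated 80% taken as given, power is about 41% per test under an assumed 21-test Bonferroni family, and about 66% to 88% for three domain scores, depending on correlation. The advantage falls to 1.28 and 1.07 times at effects of 0.5 and 0.6, is about 1.15 to 1.3 times against an any-test rule, and can reverse when few tests in a domain respond. The main reason to change the plan is that each domain would then have one pre-specified test; extra power is a likely but not guaranteed benefit.

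**What to change.** 1. Reconcile CANTAB in the Aim 1 text with Table 4, so that the test set is fixed.
2. Have the study neuropsychologist assign tests to the three domains before unblinding, using any domain column in the original Table 4.
3. Make the mean of the sign-aligned z-scores in each domain the three primary Aim 1 outcomes in the existing mixed model. State how a domain mean is formed when a test is missing at a visit.
4. Apply multiplicity control over those three outcomes and say so in place of the open-ended Bonferroni sentence.
5. Report single tests and out-of-domain measures (motor, vocabulary, reading, IADL and any span test not assigned) as secondary.

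The cost is analysis wording and one assignment exercise, with no new data. The downside is the dilution in Step 7: an effect limited to one or two tests of a domain would probably be missed, and secondary reporting does not restore confirmatory power for it. If the investigators expect such narrow effects, a pre-specified rule on a restricted set of in-domain tests would also answer H0 1.
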